Study Protocol and Statistical Analysis Plan

Study Title: SKIPPING with PAX: An Integrated Gross Motor and Social-Emotional Skill Intervention

Clinical Trial Identifier: NCT04656990

Date of the Document: July 30, 2019

SPECIFIC AIMS

The specific aims for the study include:

Aim 1: Evaluate the preliminary impact of the integrated intervention on social-emotional, behavioral, and gross motor outcomes at post-intervention (9 months after baseline).

H1: Children in the intervention condition will show significant improvements for the social-emotional, behavioral, and gross motor variables in comparison with children in the “usual classroom” control condition.

Aim 2: Evaluate the sustained impact of the integrated intervention on social-emotional, behavioral, and gross motor outcomes at three-month follow-up.

H2: Compared with the control group, the intervention group will show greater positive impact at three-month follow-up for social-emotional, behavioral, and gross motor outcomes, controlling for baseline levels.

Aim 3 (Exploratory): Explore whether baseline cognitive skills moderate intervention effects on post- and follow-up assessment of social-emotional, behavioral, and gross motor outcomes.

BACKGROUND AND SIGNIFICANCE

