Early childhood is an especially critical time for intervention to prevent modifiable risk factors such as social-emotional, behavioral, gross motor, and related difficulties from contributing to the development of more serious problems over the lifespan. Important targets include social-emotional-behavioral adjustment (e.g., interactions with others, seeking out teacher assistance, management of emotions, staying on task, behaving well in class and on the playground) and gross motor development (e.g., running, catching, jumping, and throwing), which collectively contribute to reduced risk for adverse behavioral-health, physical health, and life outcomes in adolescence and beyond. Developmental difficulties in the social-emotional, behavioral, and gross motor domains occur in all communities but can be exacerbated for children residing in predominately low-SES communities. The need for early preventive interventions to foster healthy development is amplified in calls for research to address gaps about how to effectively intervene with children experiencing lower-SES conditions and disproportionately facing health challenges. The proposed project will help to address this gap by testing whether an integrated health intervention is effective in improving social-emotional, behavioral, and gross motor outcomes for children in early childhood.

RESEARCH DESIGN, METHODS AND DATA ANALYSIS

A total of 20 preschool classrooms were randomly assigned to either the integrated intervention condition (n=10) or the control condition (n=10). Measurement took place at the level of individual children and occurred at baseline, at the end of the intervention period (i.e., 9 months after baseline), and at three-month follow-up (i.e., 12 months after baseline).

Study Population and Recruitment. The study took place in a semi-rural community in South Carolina that is in relative proximity to a metropolitan area. South Carolina provides public preschool support for Title 1 schools through the Child Development Education Program in districts across the state—of which the Early Childhood Center is a prime example. Children attending these preschool classes are four years old at time of entry, from families with an annual income of no greater than 185% of the federal poverty level. Consequently, the study sample included preschoolers residing in low socio-economic households, with 70% of the

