children qualify for free or reduced lunch. For data collection, all children in the 20 preschool classrooms were eligible for inclusion in the research sample. Parental consent was obtained to permit the child assessments.

Intervention. The intervention summarized below consisted of two components, a classroom program called PAX Good Behavior Game (PAX GBG) and a gross motor skills program called Successful Kinesthetic Instruction for Preschoolers (SKIP).

PAX GBG. Teachers first implement the GBG for a 10-minute period three days per week and then gradually increase the frequency to three 10-minute periods per day five days a week throughout the school year. Best practices for the PAX GBG indicated that while there is individual variation, teachers on average played the GBG 152 times over the school year (averaging 1488 minutes/year), with more positive outcomes in classrooms where the game is played more often.

PAX-GBG teachers participated in an orientation meeting to get an overview of the program and materials. Then, they completed a one-day online training regimen followed by two 90-minute follow-up meetings with project staff before classes began. After the program started, project staff met individually with each teacher for a brief (15 minute) check-in 3-4 times per month to support implementation and troubleshoot issues. Teachers received continuing education credit (CEUs) for their time and effort in training and mastering the PAX GBG.

SKIP. This gross motor skills training intervention is delivered on the playground by project staff to all children in the intervention classrooms. SKIP adopts an approach that teaches gross motor skills in a manner which promotes health-enhancing bouts of physical activity while fostering motivation related to social-emotional development. Children received SKIP two times per week, for 30 minutes per session, throughout the school year.

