Intervention Integrity. Research staff periodically observed intervention classrooms to document implementation fidelity for the PAX GBG. SKIP intervention sessions on the playground were digitally recorded to permit observational coding of lesson plan fidelity from the videos. Data from PAX GBG and SKIP fidelity checks were used early and throughout the intervention period to take corrective action when there were indications of slippage in intervention integrity (e.g., additional support, prompts/reminders, follow-up checks). In addition to the fidelity checks, classes of children in both the intervention and control conditions were observed periodically on the playground by research team staff. The purpose of playground/recess observation was two-fold: (1) to make sure children in the intervention condition were not receiving extra training in gross motor skills during recess periods when SKIP was not being conducted, and (2) to verify that children in the control condition were not receiving gross motor skills training that mimics SKIP.

Outcomes. The outcome measures and putative moderator measures are summarized below.

Outcome Measures. The outcome measures were collected at the three assessment time points: baseline, post-intervention period, and follow-up. The outcome measures for this study focused on gross motor skills and social-emotional skills—all considered primary outcomes. At each time point, teachers completed the Social Skills Improvement System—Rating Scales (SSIS-RS). Gross motor skills were assessed using a staff-administered Test of Gross Motor

Development-3 (TGMD-3). The testing tasks were digitally recorded and then scored by trained coders who were blinded to condition and time point. The secondary outcomes were physical activity behaviors as assessed by GT3X+ accelerometers. If possible, accelerometry data were to be captured during the school day, with logs kept to denote on and off times, and all data were to be uploaded into ActiLife Software. However, because this study was a pilot RCT rather than a fully implemented RCT, there was a distinct possibility that it would not be feasible to collect the accelerometry data.

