Putative Moderators. Three putative moderators were measured at baseline using executive-function cognitive-skills tasks from the NIH Toolbox. Attention and inhibitory control were assessed with the Flanker Task, cognitive flexibility with the Dimensional Change Card Sort Task, and working memory with the List Sorting Working Memory Task.

Demographic Data. Child's date of birth, gender, and ethnicity were acquired through school records.

Analytic Method for Aims 1 and 2. The preliminary step in the analytic plan was to examine the range and frequency distributions for all outcome variables, to transform variables, when necessary, to examine the zero-order correlations among baseline variables, and to confirm baseline equivalence for intervention and control groups. The analytic multi-level model used three-level hierarchical linear modeling (HLM), which involves time points (level 1: baseline, post, follow-up) nested within children (level 2) who are nested within classroom (level 3), to test intervention effects on each of the three outcome variables (social-emotional skills, problem behavior, and gross motor skills). Intervention condition was represented as a dummy variable (1 = intervention, 0 = control. Additional supplemental analyses were conducted for each of the outcome variables to explore whether intervention effects vary as a function of child sex.

Analytic Method for Aim 3 (exploratory). Aim 3 explored whether baseline executive-function cognitive skills moderate intervention effects on post- and follow-up assessment of social-emotional, behavioral, and gross motor outcomes. Exploratory moderator analysis was conducted by adding the putative moderators and their interactions with intervention condition and time to the overall analytic model. A separate model was estimated for each of the three putative cognitive-skills moderators.

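### Read literally, the three-level model for Aims 1 and 2 carries no classroom-by-time variation, so its condition-by-time tests are too liberal if class scores drift; adding that term and naming the 9- and 12-month contrasts is a cheap improvement

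*Combined protocol and SAP*

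**What the plan says.** Under Specific Aims, H1 concerns the end of the intervention: "Children in the intervention condition will show significant improvements for the social-emotional, behavioral, and gross motor variables", compared with usual-classroom controls. H2 concerns the three-month follow-up and is stated "for social-emotional, behavioral, and gross motor outcomes, controlling for baseline levels". Research Design, Methods and Data Analysis says that 20 classrooms were randomised, 10 to each condition, with assessments at baseline, "at the end of the intervention period (i.e., 9 months after baseline), and at three-month follow-up (i.e., 12 months after baseline".

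Analytic Method for Aims 1 and 2 gives one three-level model, "time points (level 1: baseline, post, follow-up) nested within children (level 2) who are nested within classroom (level 3", fitted to each of three outcomes with a 0/1 condition indicator. A preliminary step checks that the arms are equivalent at baseline. The paragraph does not give the time coding, the coefficient that tests H1 or H2, the way baseline is controlled, or any random effect beyond the nesting. The Aim 3 paragraph adds moderators and their interactions with condition and time to the overall model, so time is evidently a model term.

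On measurement, Outcome Measures says: "At each time point, teachers completed the Social Skills Improvement System". TGMD-3 recordings were "scored by trained coders who were blinded to condition and time point".

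**The concern.** When whole classrooms are randomised, anything that shifts a class between two occasions is part of the error against which the intervention must be judged. A classroom intercept does not capture it. That intercept is constant over time, so it cancels from any change from baseline, as does the child intercept. With only those two terms, the model judges the condition-by-time contrast against child-level residual noise, as if children in a class changed independently of one another.

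Shared change is plausible here. A teacher who becomes stricter or more lenient over the year moves the SSIS-RS scores of the whole class together. The argument from raters is weaker for the blind-coded TGMD-3, although children in a class also share a year of experience. At stake is whether the standard errors and p-values for Aims 1 and 2 reflect 20 randomised units. A lesser matter is that a reader cannot tell from the text which estimate answers which hypothesis.

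**Working it through.** The plan states no sample size, power or error-rate figure, so there is nothing to reproduce. The check sizes the effect of leaving the term out.

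**Inputs.** From the documents: 10 classrooms per arm and three occasions. Assumed: m = 10 to 20 children per class, two-sided 5% test, total variance 1, classroom variance 0.05 to 0.15, child variance 0.40 to 0.50, classroom-by-time variance v = 0 to 0.03, and residual variance e as the remainder.

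**1. True variance of a condition-by-post (or condition-by-follow-up) contrast.** The mean change in one class has variance 2(v + e/m). Comparing 10 classes with 10 gives 2 × 2(v + e/m)/10 = 0.4(mv + e)/m.

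**2. Variance reported by the model without the term.** It uses a single within-child residual with 2(20m − 2) = 40m − 4 degrees of freedom, of which 2 × 18 = 36 carry the classroom-by-time component. Its expected value is e + 36mv/(40m − 4), so the reported variance is 0.4[e + 36mv/(40m − 4)]/m.

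**3. Ratio and rejection rate.** R = (mv + e)/[e + 36mv/(40m − 4)], and the rejection rate under no effect is 2[1 − Φ(1.96/√R)].

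| m | classroom, child | v | e | R | rejection |
|---|---|---|---|---|---|
| any | any | 0 | – | 1 | 5.0% |
| 10 | 0.05, 0.40 | 0.01 | 0.54 | 0.640/0.549 = 1.17 | 7.0% |
| 15 | 0.10, 0.45 | 0.01 | 0.44 | 0.590/0.449 = 1.31 | 8.7% |
| 20 | 0.15, 0.50 | 0.01 | 0.34 | 0.540/0.349 = 1.55 | 11.5% |
| 10 | 0.05, 0.40 | 0.03 | 0.52 | 0.820/0.547 = 1.50 | 10.9% |
| 20 | 0.15, 0.50 | 0.03 | 0.32 | 0.920/0.347 = 2.65 | 22.9% |

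The m = 10 and m = 20 rows are the extremes of the assumed ranges at each value of v.

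**4. Simulation.** With 8,000 null trials per setting, rejection was 5.0% at v = 0, 8.6% in the m = 15, v = 0.01 row, and 22.4% in the m = 20, v = 0.03 row. With the term included and tested on 36 degrees of freedom it was 4.7% to 5.3%. A separate simulation, with 8 to 20 children and classroom-by-time variation at 2% to 10% of the combined classroom-by-time and residual variance, gave 6.4% to 26.4% without the term. A t test on class-mean change with 18 degrees of freedom gave 4.5% to 5.6%. Including the term but keeping the 1.96 cut-off gives 5.8% where 36 degrees of freedom apply and 6.6% where 18 apply, so the degrees of freedom matter as well.

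**5. Baseline handling.** With categorical time, the condition-by-time contrast is a difference in change, so baseline is already netted out. Let ρ be the correlation of class means between occasions. Adjusting for baseline, with the slope estimated from 20 classrooms, multiplies the variance of the change contrast by (17/16)(1 + ρ)/2. Over ρ = 0.52 to 0.91, the range implied by the assumed inputs, this runs from (17/16)(0.76) = 0.81 to (17/16)(0.955) = 1.01. That is a saving of 19% down to a loss of 1%, with a median saving of 7%.

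**The case against.** The strongest reply is that silence is not omission. The paragraph names nesting levels and does not list the random effects fitted, so a classroom-by-time term may have been included. The inflation also rests wholly on assumed variances and class sizes, and vanishes if classes do not drift. Both points stand: the documents cannot show that any test was in fact too liberal. What remains is that the model as written does not carry the term, and the design gives a specific reason to want it.

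A reader might go further and infer that time was entered as a straight line, so that an effect present at 9 months and gone at 12 would be missed. The text does not support that. It lists three discrete occasions, the aims name two time points, Aim 3 refers to effects at post and follow-up, and no slope or trajectory is mentioned.

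A reader might also infer that H2's baseline control is missing. On the natural reading, the change contrast meets it in substance, and the further gain in precision is modest.

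Nor do the documents show that teachers' baseline ratings were coloured by allocation. Intervention teachers' online training was "followed by two 90-minute follow-up meetings with project staff before classes began", but the baseline ratings are not dated against allocation or training.

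Finally, "this study was a pilot RCT rather than a fully implemented RCT", and its stated interest is preliminary impact. That lowers the stakes, but does not remove the need for standard errors that respect the randomised unit.

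**Conclusion.** The concern holds as a cheap improvement, not as a demonstrated error. The stated nesting leaves out classroom-by-time variation in a trial that randomises classrooms and has teachers rate their own pupils at each occasion. Under the assumed inputs, a nominal 5% condition-by-time test then rejects in about 7% to 11.5% of null trials at classroom-by-time variance 0.01 and 11% to 23% at 0.03. It stays at 5% if that variance is zero. Time coding, named contrasts and the form of baseline control are missing detail, since the likely reading already gives an unbiased contrast at each time point. It would be too strong to conclude that the trial's reported tests are invalid or that H2 goes untested.

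**What to change.** Write the model out:

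- Code time as categorical (baseline, post, follow-up). Test H1 by condition-by-post and H2 by condition-by-follow-up.
- Include random effects for classroom, classroom-by-time and child, with a small-sample degrees-of-freedom method suited to 20 classrooms.
- State how H2's baseline control is met. The change-from-baseline contrast suffices. A baseline-adjusted version can be reported alongside it, either by constraining baseline means to be equal across arms or by keeping only post and follow-up as outcomes with baseline as a covariate. Baseline should not be both an outcome and a covariate in the same model.
- Do not let that choice depend on the baseline-equivalence check.

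The cost is wording, a few lines of code and wider intervals; no new data are needed. From the ratios above, standard errors grow by √R: 8% to 24% at variance 0.01 (√1.17 to √1.55), and not at all at zero apart from the larger t multiplier. The analysis section is written in the past tense. If results have already been seen, disclose the model that was fitted and label the re-specified one post hoc.

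### The Aim 3 moderator models carry no age term, so if the cognitive scores are not age-adjusted, an age-dependent intervention effect could be partly credited to executive function

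*Combined protocol and SAP*

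**What the plan says.** The section Analytic Method for Aim 3 (exploratory) defines the moderator analysis in one sentence: "Exploratory moderator analysis was conducted by adding the putative moderators and their interactions with intervention condition and time to the overall analytic model". It adds: "A separate model was estimated for each of the three putative cognitive-skills moderators". The overall model, described under Analytic Method for Aims 1 and 2, is a three-level model of time points within children within classrooms, with a condition indicator. Neither section names age as a covariate or as part of an interaction. The only other effect modifier considered is sex, in supplemental analyses "to explore whether intervention effects vary as a function of child sex".

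Under Putative Moderators: "Three putative moderators were measured at baseline using executive-function cognitive-skills tasks from the NIH Toolbox". The tasks cover inhibitory control, cognitive flexibility and working memory. The type of score, raw or age-adjusted, is not given.

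On age, Study Population and Recruitment says: "Children attending these preschool classes are four years old at time of entry". Demographic Data says: "Child's date of birth, gender, and ethnicity were acquired through school records". No model is described that uses the date of birth.

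**The concern.** Children who are all four at entry can differ in age by up to about a year. It is plausible, though the documents give no figure, that performance on executive-function tasks rises with age over that span. A high unadjusted score would then partly mark an older child.

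Randomising classrooms protects the comparison of conditions. It does not protect a comparison of effects across levels of a moderator, because the moderator is not assigned. If older children gain more, or less, from the intervention for reasons of maturity, a model containing the score but not age gives part of that variation to the score.

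What is at stake is the interpretation of Aim 3. A finding that cognitive skill moderates the effect could influence whom a later, larger trial targets, when age might be the real source. Growth common to all children over the 9 to 12 months is not the issue, because the time terms absorb it. The issue is the difference in baseline age between children.

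**Working it through.** The plan states no number of children, effect size, SD or error rate for Aim 3, so there is no figure to reproduce.

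**Inputs from the document.** 20 classrooms, 10 per arm; age four at entry, hence a span of up to about 12 months; one model per task; no age term.

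**Assumed inputs.** 15 consented children per classroom; ICC 0.10; standardised outcome; one post-baseline time point (a simplified stand-in for the three-level model); correlation r of 0.2 to 0.5 between age and score; effect variation g of 0.1 to 0.3 outcome SD per SD of age; no true cognitive moderation; two-sided 5% test.

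**Step 1: the spurious slope.** Let the effect for a child of standardised age A be τ + gA. If the standardised score E has correlation r with A and the relation is linear, the mean of A given E is rE. The mean effect given E is therefore τ + r·g·E, and the score-by-condition slope is r × g.
- r = 0.2, g = 0.1: 0.02
- r = 0.3, g = 0.1: 0.03
- r = 0.5, g = 0.1: 0.05
- r = 0.3, g = 0.3: 0.09
- r = 0.5, g = 0.3: 0.15

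**Step 2: how often it reaches significance.** The within-classroom variance is 1 − 0.10 = 0.9, and each arm has 10 × 14 = 140 within-classroom degrees of freedom. The standard error of the interaction is about √(0.9/140 + 0.9/140) = 0.113. With z = slope/0.113, the rejection rate is about Φ(z − 1.96) + Φ(−z − 1.96).

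| r | g | slope | z | rate by formula | rate by simulation |
|---|---|---|---|---|---|
| 0.2 | 0.1 | 0.02 | 0.18 | 5.4% | 5.1% |
| 0.3 | 0.1 | 0.03 | 0.26 | 5.8% | 5.5% |
| 0.5 | 0.1 | 0.05 | 0.44 | 7.3% | 7.1% |
| 0.3 | 0.3 | 0.09 | 0.79 | 12% | 10.4–11.5% |
| 0.5 | 0.3 | 0.15 | 1.32 | 26% | 23–24.6% |

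The formula runs slightly high because it ignores the extra residual variance that omitted age creates. Class size matters too: with an ICC of 0.05, r = 0.5 and g = 0.3, simulation gives 18%, 24% and 33% for 10, 15 and 20 children per classroom.

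**Step 3: how large these values of g are.** If ages are roughly uniform over 12 months, one SD is 12/√12 = 3.46 months, and the whole span is 12/3.46 = 3.46 SD. So g = 0.1 means the effect differs by 0.35 outcome SD between youngest and oldest, and g = 0.3 means 0.3 × 3.46 = 1.04 SD, which is large.

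**Step 4: what removes it.** With age and age-by-condition added, the simulated slope is about 0 and the rate 4–6%. Adding age only as a main effect does not help: at r = 0.5, g = 0.3, ICC 0.05 and 20 children per classroom, the slope stays at 0.153 and the rate at 33%. If the scores are already age-adjusted, or r = 0, or g = 0, the slope is about 0 and the rate stays near 5%.

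**Step 5: the price.** Adjustment multiplies the interaction's standard error by about 1/√(1 − r²): 1.05 at r = 0.3 and 1.15 at r = 0.5.

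**The case against.** A reader might infer that any age-dependent effect would be reported as cognitive moderation, or that Aim 3 cannot separate skill from age at all. The documents support neither. The mechanism needs unadjusted scores, a correlation with age inside a one-year band, and a real age-dependent effect. The plan is silent on the first and gives no information on the other two. Even then only the fraction r of the age effect carries over, and at g = 0.1 the inflation is hard to see.

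A reader might also infer that agreement across the three tasks would be a frequent false replication. Assuming the tasks correlate 0.2 given age, all three models are falsely significant in 0.8% of trials at r = g = 0.3, and in 6.5% at r = 0.5, g = 0.3. At least two of the three are significant in 6% and 20% of trials respectively (0.8% and 0.7% with age terms). This is a concern mainly at the extreme end of the assumptions.

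The strongest counter-argument concerns the question asked. If Aim 3 only describes which children benefit more, a score that stands in for age still describes that correctly, and the result is not false. It misleads only when read as a role for executive function distinct from age. Nor does adjusting for age make the moderation causal, since other correlates of the score remain. This stands, and it is why the planned model should be kept rather than replaced.

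Finally, age might enter the preliminary correlations or the baseline-equivalence check. Nothing excludes that, but neither step adjusts the moderator contrast. The gap in the stated models therefore remains.

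**Conclusion.** The point holds in a conditional form. No age term or age interaction is specified for Aim 3 although date of birth is held, and the score type is not stated. If the scores are unadjusted and the intervention effect varies with age, part of that variation, about r × g, could be attributed to executive function. Under the assumed design the false-positive rate is close to nominal for a modest age-dependent effect. It reaches roughly 11% to 24% only when the effect differs by about 1 SD between the youngest and oldest child. All values of r, g, class size and ICC are assumptions. If age-adjusted scores were used, the problem largely disappears. The analysis is exploratory within a pilot, so the consequence is confined to how Aim 3 is interpreted.

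**What to change.** - State whether each cognitive score is raw or age-adjusted.
- For each Aim 3 model, also fit a version that adds baseline age, from the date of birth already held, with the same interactions with condition and time that the cognitive score receives. A main effect of age alone is not enough.
- Report this version beside the planned model. Attribute moderation to executive function rather than age only if the interaction persists in the age-adjusted version. Otherwise describe the score as identifying who benefits, without separating it from age.

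The cost is a few extra terms per exploratory model and a wider interval on the cognitive interaction, by about 5% at r = 0.3 and 15% at r = 0.5. No new data are needed. Because the document is written in the past tense, this can be done as a supplementary analysis, labelled as such.
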